7.3.9.2 Electrocardiogram

Electrocardiogram (ECG) recording will be performed as per the site's local practice. A standard 12-lead ECG will be recorded after the subject has rested for at least 10 minutes in a supine position.

The following parameters will be documented: heart rate, PR interval, QRS interval, QT interval, and QT interval corrected by the ECG machine according to Bazett's formula and Federici's formula. Every ECG has to be assessed as normal, abnormal – clinically not relevant, or abnormal – clinically relevant. A diagnosis has to be provided on the eCRF for all ECGs assessed as abnormal – clinically relevant. All ECG print-outs will be interpreted by a qualified physician. Any print-outs of ECGs on thermo-sensitive paper must be photocopied and stapled together for inclusion in the source documents and signed by Principal Investigator or designee.

See [Appendix A](#) for the timepoints of assessment.

7.3.9.3 Chest X-ray

A chest X-ray (anterior-posterior and left lateral views) will be assessed during the Screening Period to exclude subjects with relevant pulmonary diseases. Subjects will be referred to a radiology facility (within or outside the investigational site) for this procedure. No new examination is required if the subject can present a chest X-ray with anterior-posterior and left lateral views at the Screening Visit which is not older than 6 months.

7.4 Biomarker Assessment

All bioanalytical assays and laboratory assessments (section 7.5) will be carried out using validated methods. The bioanalytical methods used will be documented in the bioanalytical reports. A list of laboratories is provided in [Appendix B](#).

Precautions should be taken during blood sampling and processing to prevent the contamination of samples with environmental nicotine or CO.

Confidentiality Statement

Data and information contained in this document are considered to constitute trade secrets and confidential commercial information, and the legal protections provided to such trade secrets and confidential information are hereby claimed under the provisions of applicable law. No part of this document may be publicly disclosed without the written consent of Philip Morris Products S.A.

7.4.1 Biomarker of Exposure

7.4.1.1 Biomarker of Exposure to CO and COHb

COHb measured in blood and exhaled CO will be investigated as a measure of exposure to CO.

- CO breath test:

CO in exhaled breath will be measured using the Smokerlyzer[®] (e.g., Micro 4 Smokerlyzer[®] device or similar).

A CO breath test will be conducted once per day, preferably in the evening around 8:00 PM. The CO breath test should be conducted in timely conjunction with the blood sampling for COHb.

See [Appendix A](#) for the timepoints of assessment.

- COHb test:

Tests for COHb measurement will be performed at a designated laboratory. One blood sample will be taken in the evening around 8:00 PM. The COHb sampling should be conducted in timely conjunction with the CO breath test.

See [Appendix A](#) for the timepoints of assessment.

7.4.1.2 Plasma Nicotine and Cotinine

Nicotine and cotinine concentrations will be measured in plasma to evaluate the exposure to nicotine.

One blood sample in subjects in the CHTP 1.0 and CC arm will be taken in the evening around 8:00 PM.

See [Appendix A](#) for the timepoints of assessment.

7.4.1.3 Biomarkers of Exposure to HPHCs

The following BoExp to HPHCs will be measured in 24-hour urine collection samples as per the schedule of events ([Appendix A](#)):

- Primary endpoints: MHBMA, 3-HPMA, S-PMA.
- Secondary endpoints: total 1-OHP, total NNN, 4-ABP, 1-NA, 2-NA, o-tol, CEMA, HEMA, 3-hydroxybenzo(a)pyrene, 3-HMPMA, total NNAL, NEQ.

Confidentiality Statement

Data and information contained in this document are considered to constitute trade secrets and confidential commercial information, and the legal protections provided to such trade secrets and confidential information are hereby claimed under the provisions of applicable law. No part of this document may be publicly disclosed without the written consent of Philip Morris Products S.A.

BoExp to HPHCs in urine will be expressed as quantity excreted, and their concentrations will be adjusted to creatinine. For normalization of BoExp to HPHCs, creatinine will also be measured in the 24-hour urine samples.

7.4.2 CYP1A2 Activity Test

CYP1A2 activity will be assessed in plasma by measuring paraxanthine (PX) and caffeine (CAF) concentrations and calculating the PX/CAF molar metabolic ratio. Samples to measure PX and CAF will be drawn approximately 6 hours (± 15 minutes) after the intake of a cup of coffee made from 4.2 g ($\pm 10\%$) regular instant coffee (Nescafé Gold Instant; Nestlé; Deutschland; CAF content: 72 mg/2 g) with 150 ml ± 10 ml water. The CAF content will be approximately 150 mg CAF (11).

The exact time of intake of the cup of coffee in the morning and of the time of blood sampling 6 hours [± 15 minutes] later must be recorded.

See [Appendix A](#) for the timepoints of assessment.

7.4.3 CYP2A6 Activity Test

CYP2A6 activity will be measured in plasma using the molar metabolic ratio of *trans*-3'-hydroxycotinine to cotinine. CYP2A6 activity drives the metabolism of nicotine to cotinine and subsequent metabolites. CYP2A6 blood sampling has to be done prior to smoking.

See [Appendix A](#) for the timepoints of assessment.

7.4.4 Ames Mutagenicity Test

Urine mutagenicity, a biomarker for measuring mutagen load, will be measured in 24-hour urine.

The urinary determination of each sample will be done in one bacterial strain (*S. typhimurium* strain YG1024) using S9 metabolic activation and 4 doses for each of the urine extracts.

See [Appendix A 1](#) for the timepoints of assessment.

7.5 Laboratory Assessments

A list of laboratories is provided in [Appendix B](#).

7.5.1 Clinical Chemistry, Hematology, and Urine Analysis for Safety Panel

Hematology, clinical chemistry, and urine analysis for the safety panel will be measured at Screening, on Day -1 and at Discharge on Day 6 (Day of Discharge). Tests will be conducted at a local laboratory or the site. Blood will be taken after no less than the 10 hours of fasting

Confidentiality Statement

Data and information contained in this document are considered to constitute trade secrets and confidential commercial information, and the legal protections provided to such trade secrets and confidential information are hereby claimed under the provisions of applicable law. No part of this document may be publicly disclosed without the written consent of Philip Morris Products S.A.

except at the Screening Visit (section 6.7.2). The urine test/urine analysis safety panel will be performed at a local laboratory. Parameters to be measured are listed in Table 3.

Table 3 Hematology and Clinical Chemistry Parameters (Safety)

Hematology	Clinical Chemistry	Urine Analysis
- Hematocrit	- Albumin	- pH
- Hemoglobin	- Total protein	- Bilirubin
- Mean corpuscular hemoglobin	- Alkaline phosphatase	- Glucose
- Mean corpuscular hemoglobin concentration	- Alanine aminotransferase	- Nitrite
- Mean corpuscular volume	- Aspartate aminotransferase	- Red blood cell traces
- Platelet count	- Blood urea nitrogen	- Protein
- Red blood cell count	- Creatinine	- Specific gravity
- White blood cell (WBC) count	- Gamma-glutamyl transferase	- Urine sediment
- Differential WBC count:	- Fasting glucose	
• Neutrophils	- Lactate dehydrogenase	
• Basophils	- Potassium	
• Eosinophils	- Sodium	
• Lymphocytes	- Total bilirubin	
• Monocytes	- Direct bilirubin	
	- Total cholesterol	
	- Triglycerides	

See [Appendix A](#) for the timepoints of assessment.

7.5.2 Serology

A test for hepatitis B surface antigen, hepatitis C virus and human immunodeficiency virus (anti-HIV1/2 and p24 antigen) will be done. In case of positive results, the subject will be referred to appropriate medical care.

See [Appendix A](#) for the timepoints of assessment.

7.5.3 Urine Drug Screening

The urine will be screened for the following drugs or class or drugs: amphetamines, barbiturates, benzodiazepines, cannabinoids, cocaine and opiates.

See [Appendix A](#) for the timepoints of assessment.

Confidentiality Statement

Data and information contained in this document are considered to constitute trade secrets and confidential commercial information, and the legal protections provided to such trade secrets and confidential information are hereby claimed under the provisions of applicable law. No part of this document may be publicly disclosed without the written consent of Philip Morris Products S.A.

7.5.4 Urine Cotinine Screening

A urine dip-stick or cassette cotinine test will be performed to confirm the subject's smoking status. The test must detect cotinine with a cotinine threshold of ≥ 200 ng/mL, (e.g., One-Step Cotinine Test 008A086, Ultimed, Belgium).

See [Appendix A](#) for the timepoints of assessment.

7.5.5 Alcohol Breath Test

Subjects will undertake a breath alcohol test using an alcometer device (e.g., Alcotest 7410 Plus, Dräger).

See [Appendix A](#) for the timepoints of assessment.

7.5.6 Urine Pregnancy Test

All female subjects will have pregnancy testing at the Screening Visit, at Admission to the clinic and at Discharge. Female subjects with a positive pregnancy test at the Screening Visit or at Admission will not be enrolled and will be considered as screen failures. In case of any positive urine pregnancy test, the Investigator or designee will inform the subject about the risks associated with smoking during pregnancy.

The post-menopause is formally defined as the time after which a woman has experienced 12 consecutive months of amenorrhea (lack of menstruation) without a period. If a woman claims she is post-menopausal, but has had her menses within 12 months, a follicle stimulating hormone test must be performed and must be within acceptable limits of the post-menopausal status. When the post-menopausal status of a female is confirmed, the pregnancy test scheduled during the study will not be done.

In the event of an unclear urine pregnancy test, absence of pregnancy should be confirmed by a serum follicle stimulating hormone level >20 IU/l.

All pregnancies detected during the study must be reported and handled as described in section [8.5](#).

See [Appendix A](#) for the timepoints of assessment.

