5.2 Exclusion Criteria

Subjects who meet any of the following exclusion criteria must not be enrolled into the study:

Exclusion Criteria	Rationale	Screening	Admission (Day -3)
1. As per the Investigator (or designee) judgment, the subject cannot participate in the study for any reason (e.g., medical, psychiatric and/or social reason).	Safety	X	X
2. The subject is legally incompetent, physically or mentally incapable of giving consent (e.g., emergency situation, under guardianship, in a social or sanitary establishment, prisoner or involuntarily incarcerated).	Administrative	X	
3. Clinically relevant gastrointestinal, renal, hepatic, neurological, hematological, endocrine, oncological, urological, pulmonary, immunological, psychiatric or cardiovascular disorders or any other conditions that in the opinion of the investigators would jeopardize the safety of the participant or affect the validity of the study results.	Safety	X	
4. Abnormal findings on physical examination, in the medical history, or in clinical laboratory results deemed clinically relevant by investigators (as per the common terminology criteria for adverse events [CTCAE]).	Safety	X	X
5. The subject has (FEV ₁ /FVC) < 0.7 and FEV ₁ < 80% of the predicted value at post-bronchodilator spirometry.	Safety	X	
6. The subject has asthma condition (FEV ₁ /FVC < 0.75 and reversibility in FEV ₁ > 12% (or > 200 mL) from pre- to post-bronchodilator values).	Safety	X	
7. The subject has a body mass index (BMI) < 18.5 or ≥ 32 kg/m ² .	Safety	X	

Confidentiality Statement

Data and information contained in this document are considered to constitute trade secrets and confidential commercial information, and the legal protections provided to such trade secrets and confidential information are hereby claimed under the provisions of applicable law. No part of this document may be publicly disclosed without the written consent of Philip Morris Products S.A.

Exclusion Criteria	Rationale	Screening	Admission (Day -3)
8. As per the Investigator's or designee's judgment, the subject has medical conditions which require or will require in the course of the study, a medical intervention (e.g., start of treatment, surgery, hospitalization) which may interfere with the study participation and/or study results.	Effect	X	X

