* Intrauterine device, intrauterine system, barrier methods of contraception (condoms, occlusive caps) with spermicidal foam/gel/film/suppository vasectomized partner(s), or true abstinence (periodic abstinence and withdrawal are not effective methods) from Screening until the end of the Safety Follow-up Period plus up to 3 days. . Hysterectomy, tubal ligation, bilateral oophorectomy or post-menopausal status are reasons for not needing to use birth control. Post-menopausal status is defined as women who have not experienced menses for greater than 12 months. If a woman claims she's post-menopausal, but has had her menses within 12 months, a follicle stimulating hormone test must be performed and must be within acceptable limits.

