5.5 Violation of Selection Criteria

Any subjects who do not meet the entry criteria after signing the ICF and prior to Enrolment at Day -3 will be considered as screen failures and will be replaced by other subjects. Re-screening of subjects will not be permitted.

Confidentiality Statement

Data and information contained in this document are considered to constitute trade secrets and confidential commercial information, and the legal protections provided to such trade secrets and confidential information are hereby claimed under the provisions of applicable law. No part of this document may be publicly disclosed without the written consent of Philip Morris Products S.A.

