7.3.4 Demonstration and CHTP 1.0 Test

All subjects will have a demonstration of CHTP 1.0 at the Screening Visit. On Day -3 after enrollment, subjects will have a product test, using up to 5 sticks of CHTP 1.0. Only subjects willing and ready to use CHTP 1.0 will continue in the study.

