9.1 Screening Visit

The Screening Visit will be performed within 6 weeks (1 to 42 days) prior to Admission. First, the ICF along with study information should be given to the subject. When/if the ICF is signed, dated and timed, the other screening procedures can be performed in the order deemed most practical. The point of time of each screening procedure must be recorded in the source document. While it is recommended to complete as many screening procedures as possible in one day, it is permissible to complete those over more than one day. Smoking is allowed during the Screening Visit.

[Table 6](#) shows the procedures for the Screening Visit. The sequence of assessments/events is given just for illustrative purposes and will be at the discretion of the site after signature of the ICF.

Table 6 Time Schedule – Screening Visit (Day -45 to Day -3)

Time	Blood Sample	Procedures	Additional Information
Start of Procedure		Screening	
Before any study procedure		Informed consent for study participation and additional consents for bio-banking (if applicable)	
During the visit	√	Clinical laboratory parameters (hematology, clinical chemistry)	

Confidentiality Statement

Data and information contained in this document are considered to constitute trade secrets and confidential commercial information, and the legal protections provided to such trade secrets and confidential information are hereby claimed under the provisions of applicable law. No part of this document may be publicly disclosed without the written consent of Philip Morris Products S.A.

Time	Blood Sample	Procedures	Additional Information
Start of Procedure		Screening	
During the visit	√	Serology (HIV, hepatitis B and C)	
During the visit		Information on the risks of smoking, smoking cessation advice and debriefing.	
During the visit		Demographic data collected	
During the visit		Questions about smoking history/habits and Intention to quit smoking	
During the visit		Medical history/concomitant disease, prior and concomitant medication	
During the visit		Identification of currently used CC brand	
During the visit		FTND questionnaire	
During the visit		ECG	At least 10 minutes in supine position prior to recording
During the visit		Chest X-ray	If not performed 6 months prior to Screening
During the visit		Vital signs (blood pressure, pulse rate, respiratory rate)	At least 5 minutes in supine position
During the visit		Safety urine analysis	
During the visit		Urine pregnancy test (females only)	

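### After an unclear urine pregnancy test the protocol names only serum FSH above 20 IU/l as confirmation, so a non-pregnant woman at or below that level cannot be confirmed as not pregnant

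*Protocol*

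**What the plan says.** Protocol 7.5.6 schedules a urine pregnancy test at Screening, Admission and Discharge. The first two decide eligibility: "Female subjects with a positive pregnancy test at the Screening Visit or at Admission will not be enrolled". Women past the menopause are exempt: "When the post-menopausal status of a female is confirmed, the pregnancy test scheduled during the study will not be done".

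For a result that is neither clearly positive nor clearly negative, the section gives one instruction: "In the event of an unclear urine pregnancy test, absence of pregnancy should be confirmed by a serum follicle stimulating hormone level >20 IU/l".

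FSH has a different purpose elsewhere. In the preceding paragraph of 7.5.6, and in the footnote to exclusion criterion 21 (Protocol 5.2, repeated in SAP 6.2.2), it checks a woman who says she is post-menopausal but has menstruated within 12 months: "a follicle stimulating hormone test must be performed and must be within acceptable limits".

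**The concern.** The sentence appears to put a test of menopausal status where a pregnancy test belongs. The women it reaches are those not already confirmed as post-menopausal, and for them a low FSH leaves the question open whether or not they are pregnant.

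What is at stake is an eligibility and participant-safety check. Use of the investigational product follows closely on enrolment: "On Day -3 after enrollment, subjects will have a product test, using up to 5 sticks of CHTP 1.0". If the named test cannot give an answer, the site has two ways out. It can exclude the woman. Protocol 5.5 says that subjects failing entry criteria before enrolment "will be considered as screen failures and will be replaced by other subjects. Re-screening of subjects will not be permitted", so she loses her place for good. Or it can enrol her without the confirmation that 7.5.6 asks for.

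**Working it through.** There is no power or alpha calculation to reproduce. The check is a comparison of texts, followed by a rough count.

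**Texts side by side**

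| Place | Use of FSH or pregnancy test |
|---|---|
| Protocol 7.5.6, second paragraph | FSH for menopausal status; women confirmed as post-menopausal skip the pregnancy test |
| Protocol 5.2, criterion 21 footnote; SAP 6.2.2, same footnote | FSH for menopausal status |
| Protocol 7.5.6, unclear-test sentence | FSH above 20 IU/l to confirm absence of pregnancy |
| Protocol 5.2, criterion 20 | Refers to positive tests; silent on unclear ones |
| Protocol Tables 6, 7, 15 and 16; Table A1 | Pregnancy test is a urine test or is listed without a serum alternative |
| Protocol Table 3 (safety panel) | Neither FSH nor a serum pregnancy test |

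**Reasoning**

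1. The unclear-test rule applies only to women who are tested, that is, women not confirmed as post-menopausal.
2. By its wording, FSH above 20 IU/l confirms absence of pregnancy. FSH of 20 IU/l or below confirms nothing.
3. No other confirmatory test is named, so a non-pregnant woman with FSH of 20 IU/l or below has no stated route to confirmation.

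This is conditional on her FSH and needs no outside figure for typical levels.

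**How often**

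Inputs from the documents:
- two of the three scheduled tests bear on eligibility (Screening and Admission);
- about 80 subjects, with each sex at least 40% (Protocol 5).

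Assumptions, not in the documents:
- 0.5% to 2% of tests are unclear;
- 50% to 100% of the women concerned have FSH of 20 IU/l or below.

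Affected results = tests × unclear rate × share with FSH of 20 IU/l or below.

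- Per 100 women tested at both visits: 200 × 0.005 × 0.5 = 0.5, up to 200 × 0.02 × 1.0 = 4.0.
- Women implied by the quota: 0.40 × 80 = 32, up to 80 − 32 = 48.
- Eligibility tests in those women: 32 × 2 = 64, up to 48 × 2 = 96. These are upper limits for these women, because those confirmed as post-menopausal are not tested.
- Unclear tests: 64 × 0.005 = 0.32, up to 96 × 0.02 = 1.92.
- Affected results: 0.32 × 0.5 = 0.16, up to 1.92 × 1.0 = 1.92.

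The number of women screened is not stated. Women screened but not randomised add to this count.

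**The case against.** The strongest reply is that little follows from the error.

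- **The rule is worded as a recommendation.** It says *should*, whereas the menopause paragraph says *must*. Nothing forbids repeating the urine test.
- **There is room to resolve the result.** Protocol 9.1 says of the Screening procedures that "it is permissible to complete those over more than one day", and a second urine test is compulsory at Admission before enrolment. The gap is therefore mainly an unclear result at Admission.
- **Other safeguards exist.** Contraception is required, and exclusion criterion 1 lets the site decline anyone: "As per the Investigator (or designee) judgment, the subject cannot participate in the study for any reason (e.g., medical, psychiatric and/or social reason".
- **The cautious outcome of an unconfirmed result is not to enrol.** That costs one candidate, who is replaced.
- **The count rests on assumed rates.** At its low end the problem may never arise.
- **The remedy needs a fast laboratory result.** Protocol 7.6 sends blood outside the safety panel to a central laboratory, and enrolment and the product test both fall on Day -3.

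Most of this stands as a limit on frequency and consequence. The Admission retest does reduce the weight of an unclear Screening result, so a count over both visits overstates the cases that matter most. But none of these points supplies a confirmation. Discretion, contraception and an unmentioned repeat test are not what 7.5.6 names, and none resolves an unclear result on Day -3. The turnaround difficulty applies equally to the FSH sample the protocol already asks for.

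**Conclusion.** The concern holds. The rule as written cannot do its job for a non-pregnant woman with FSH of 20 IU/l or below, and the documents give her no other stated outcome. That conclusion rests on the wording alone.

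The practical size is small: about 0.2 to 1.9 affected eligibility results on the quota proxy, or 0.5 to 4 per 100 women tested at both visits, and both ranges depend wholly on the assumed rates. There is no effect on the primary endpoints or power. A correction should be made because this is an eligibility and safety check with the wrong test named, not because it threatens the trial's results.

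**What to change.** Replace the FSH sentence in Protocol 7.5.6 with wording such as: *If a urine pregnancy test is unclear, pregnancy is to be ruled out by a negative serum pregnancy test; at Admission the result must be available before enrolment and product use.* Leave FSH in the menopausal-status paragraph and in the criterion 21 footnote. It would help to state which laboratory runs the test, since Protocol 7.6 does not provide a local route for either assay.

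The cost is one sentence, submitted to the ethics committee as an amendment under Protocol 1.1. The serum pregnancy test takes the place of the for-cause FSH sample, so no extra blood draw is needed. The drawback is that the rare woman with an unclear Admission test waits for her result and could miss her slot if it is slow.
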